2.3 STUDY OUTCOMES

The following outcomes will be tracked for the trial:

Primary outcome is: the proportion of patients alive and free of respiratory failure (not requiring non-rebreather, high-flow nasal cannula, non-invasive positive pressure ventilation, or mechanical ventilation) at 28 days

- A. Primary safety outcome: Occurrence of intracranial bleeding or major bleeding (Definition: A bleeding episode leading to hemodynamic compromise requiring emergency intervention (such as replacement of fluid and/or blood products, inotropic support, or surgical treatment), or life-threatening or fatal bleeding) within 72 hours of randomization. All outcomes will be assessed in a blinded fashion by the DSMC/CEC.
- B. Secondary outcomes include: 14-day in-hospital mortality, 28-day mortality, ventilator-free days, respiratory failure-free days (not requiring NRB, HFNC, NIPPV, or mechanical ventilation), vasopressor-free days, vasopressor requirements at 24 and 72 hours, P/F ratio at 24 hours and 72 hours, ICU-free days, hospital length of stay, new renal failure, need for renal replacement therapy
- C. Mortality: given a high mortality rate amongst this patient population, patients who die will be included in statistical analysis. Variables of interest will be calculated until the point these patients expire.

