 - All women of childbearing potential will have a pregnancy test at screening. If a urine pregnancy test is positive, it must be confirmed by a serum pregnancy test.

- SARS-CoV-2 PCR Test**

A SARS-CoV-2 PCR Test will be conducted during screening to determine if the patient is COVID positive.

- Respiratory Status / Ventilator Settings**

Respiratory or Ventilator settings will be collected at Screening.

Tenecteplase–Icahn School of Medicine at Mount Sinai
Protocol ML42492

- Ventilator settings (if appropriate): RR, TV, PI (if PCV or PSV) FiO2, PEEP, Plateau Pressure
- NIPPV settings (if appropriate): RR, IPAP, EPAP, FiO2
- HFNC settings (if appropriate): FiO2, flow
- NRB settings (if appropriate): flow
- **Ordinal Scale Assessment**

The Ordinal Scale Assessment will be conducted daily to determine the patient's current status.

- **Imaging**

If the patient has a standard of care CT Scan or X-Ray performed, the imaging result will be captured in the Screening CRF.

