4.5.5 Follow Up Period (Day 4 -27)

The subject will have a daily follow up collecting all of the below assessments. If the patient reaches an aPTT value of 70-90 seconds, subsequently daily aPTT values will be record until discharge or Day 28.

- Neurological Exam

- Vitals

- Laboratory Samples (Standard of care)

- Respiratory Status / Ventilator Settings

- Ordinal Scale Assessment

- Imaging (Standard of Care)

- Concomitant medication review (excluding “prn” or “as needed” medications)

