4.5.6 End of Study (Day 28)

The following assessments will be collected at the final End of Study timepoint if the patient is still admitted:

- Neurological Exam

- Vitals

- Laboratory Samples (Standard of care)

Tenecteplase–Icahn School of Medicine at Mount Sinai
Protocol ML42492

20

Thromboelastograms (when available according to standard practice)

- Respiratory Status / Ventilator Settings
- Imaging (Standard of Care)
- Concomitant medication review (excluding “prn” or “as needed” medications)

The ordinal scale assessment will be completed at day 28 regardless of whether the patient is admitted or discharged.

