6.2 PRIMARY EFFICACY VARIABLE

Data will be analyzed according to clinical status at day 28. Outcome will be the proportion of patients who are alive and free of respiratory failure (no use of HFNC, NIPPV, Intubation). All other patients, those on HFNC, NIPPV, or mechanical ventilation, or dead, will be assessed as

Tenecteplase-Icahn School of Medicine at Mount Sinai
Protocol ML42492

37

failures for the purposes of the primary analysis. In the case of missing data, a last carry forward methodology will be used.

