
Tenecteplase-Icahn School of Medicine at Mount Sinai
Protocol ML42492

45

Appendix 1

Study Flowchart

	Screening	Enrollment/Randomization ^a		Follow Up Period (Day 4 to 27 post randomization)	End of Study (Day 28 OR Discharge)
		Pre-Randomization (must be collected within 2 h of study drug administration)	Post Randomization q6 hr. to 72 hr.		
Informed Consent	x				
Demographics	x				
Medical History	x				
Inclusion/Exclusion Criteria	x	x			
Weight for Dosing	x				
Vital Signs ^b	x	x	x	x	x
PCR COVID Test	x				
Lab Testing ^c	x	x	x ^d	SOC	SOC
Arterial Blood Gas ^e	x	x	x [*]	SOC	
Respiratory Status/Ventilator Settings ^f	x	x	x	x ^{**}	x
Ordinal Scale	x	x	x	x	x
Neurological Exam ^g	x	x	x	x	x
Vasopressor Dosing	x	x	x	x	
TNK-tPA Dosing			x		
Heparin Dosing ^h	x***	x***	x	x	
Imaging ⁱ	SOC		SOC	SOC	SOC
Pregnancy Test ^j	x				
Adverse Events/ SAE Review ^k	x	x	x	x	x
Concomitant Medications	x	x	x	x	x

Tenecteplase–Icahn School of Medicine at Mount Sinai
Protocol ML42492

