- j. A woman is considered to be of childbearing potential if she is postmenarcheal, has not reached a postmenopausal state (\geq 12 continuous months of amenorrhea with no identified cause other than menopause), and has not undergone surgical sterilization (removal of ovaries and/or uterus). Urine/serum pregnancy test: all women of childbearing potential will have a pregnancy test at screening. If a urine pregnancy test is positive, it must be confirmed by a serum pregnancy test.
- k. All AEs that occur after signing the ICF and up to the EOS visit must be recorded. AESI's for this study protocol include: bleeding, hypersensitivity, thromboembolism, cholesterol embolization and arrhythmias. post-permanent SD discontinuation.
 - * To be performed q12h.
 - ** To be performed daily until a 2 point improvement in the ordinal scale assessment OR until 27 days OR until death OR discharge.
 - *** For patients already on heparin.

Tenecteplase—Icahn School of Medicine at Mount Sinai
Protocol ML42492

47

Effective Date: 6/15/2021

End Date: 12/7/2021

Appendix 2

Safety Reporting Fax Cover Sheet

A Member of the Roche Group

SAFETY REPORTING FAX COVER SHEET

GENENTECH SUPPORTED RESEARCH

AE / SAE [contact]

Genentech Study Number	
Principal Investigator	
Site Name	
Reporter name	
Reporter Telephone #	
Reporter Fax #	

Initial Report Date	[DD] / [MON] / [YY]
Follow-up Report Date	[DD] / [MON] / [YY]

Patient Initials (Enter a dash if patient has no middle name)	[] - [] - []
--	-----------------

SAE or Safety Reporting questions, contact Genentech Drug Safety: [contact]

PLEASE PLACE MEDWATCH REPORT or SAFETY REPORT BEHIND THIS COVER SHEET

Appendix 3

FDA MedWatch 3500 Form

This form is included in the study start-up zip file to be sent to sites via email.

Tenetecplase-Icahn School of Medicine at Mount Sinai
Protocol **ML42492**

49

Effective Date: 6/15/2021

End Date: 12/7/2021

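### Appendix 1 lets daily respiratory-status recording stop at a 2-point gain on an ordinal scale whose levels are not given; Section 4.5.5 does not, and two free-day outcomes depend on which is followed

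*Combined protocol and SAP*

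**What the plan says.** Section 4.5 makes Appendix 1 the schedule of activities and requires every activity in it to be performed and documented.

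- **Appendix 1, flowchart and footnote \*\*.** The row "Respiratory Status/Ventilator Settings" carries a double asterisk in the Day 4 to 27 column only. The footnote says: "To be performed daily until a 2 point improvement in the ordinal scale assessment OR until 27 days OR until death OR discharge". The Ordinal Scale, Vital Signs and Vasopressor Dosing rows have a plain mark in that column.
- **Section 4.5.5 (Day 4 to 27).** "The subject will have a daily follow up collecting all of the below assessments". The list that follows includes both respiratory status and the ordinal scale, with no early stop for either.
- **Section 4.5.2.** This is the nearest the text comes to describing the scale: "The Ordinal Scale Assessment will be conducted daily to determine the patient's current status". No levels, direction or named instrument are given.
- **Section 4.5.6 (Day 28).** Respiratory status falls under this condition: "The following assessments will be collected at the final End of Study timepoint if the patient is still admitted". The scale does not: "The ordinal scale assessment will be completed at day 28 regardless of whether the patient is admitted or discharged".
- **Section 2.3.** The secondary outcomes include "ventilator-free days, respiratory failure-free days (not requiring NRB, HFNC, NIPPV, or mechanical ventilation), vasopressor-free days".
- **Section 6.2.** For the primary variable: "In the case of missing data, a last carry forward methodology will be used".

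**The concern.** Two parts of one protocol give sites different instructions for the same data item. The shorter instruction ends collection at an event, a 2-point gain, that sites cannot apply uniformly without knowing the scale's levels and the assessment from which the gain is measured.

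The item matters because two secondary outcomes are counts of days defined by device. A 2-point gain is not shown to mean that the patient has left respiratory failure. Someone could still be on high-flow nasal cannula or a non-rebreather mask when recording stops, and the later day of coming off it would not appear on this row. A return to a device after a first improvement would not appear either, because nothing restarts the recording. The gap falls only on patients who improve, so it is related to outcome.

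**Working it through.** There is no stated figure to reproduce. The check compares the texts and counts the uncovered days.

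**Step 1. The two schedules for respiratory status, Days 4 to 27**

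| Feature | Appendix 1, footnote \*\* | Section 4.5.5 |
|---|---|---|
| Frequency | Daily | Daily |
| Stops at a 2-point ordinal gain | Yes | No |
| Reference assessment for the gain | Not stated | Not applicable |
| Gain must be sustained | Not stated | Not applicable |
| Restarts on worsening | Not stated | Not applicable |

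Both cannot be followed for a patient who gains 2 points while still in hospital.

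**Step 2. Size of the gap under the footnote**

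The follow-up period has 27 − 4 + 1 = 24 days. If the last record is on day k, days k+1 to 27 have no scheduled entry on this row, so the gap is 27 − k days. Day 28 is not counted, because 4.5.6 collects respiratory status that day in anyone still admitted.

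| Last record (day k) | Days without an entry (27 − k) | Share of 24 days |
|---|---|---|
| 4 | 23 | 96% |
| 7 | 20 | 83% |
| 8 | 19 | 79% |
| 10 | 17 | 71% |
| 14 | 13 | 54% |
| 21 | 6 | 25% |

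The stop days are illustrations for a patient who stays in hospital to day 27. The documents give no expected time to a 2-point gain. Under 4.5.5 the gap is 0 for a patient who is still followed.

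**Step 3. Which outcomes use this row**

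- Ventilator-free days need ventilator status each day. Respiratory failure-free days need to know each day whether the patient requires a non-rebreather mask, high-flow nasal cannula, non-invasive positive pressure ventilation or mechanical ventilation. Both are exposed.
- Vasopressor-free days use vasopressor doses, which Section 4.5.4 and the flowchart collect separately, daily after 72 hours. ICU-free days do not use this row. Neither is exposed.
- The day-28 primary outcome is less exposed. Inpatients have respiratory status recorded that day. For discharged patients, the ordinal scale is the only respiratory information that 4.5.6 schedules at day 28 itself.

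**Step 4. Whether the daily ordinal scale fills the gap**

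It stays scheduled daily after the gain. It can replace the device record only if its levels separate the four devices in Section 2.3 from lesser support. The supplied text does not show this. The protocol's list of tables and appendices contains no ordinal scale. The separation cannot be assumed for the non-rebreather mask in particular: Sections 2.2 and 2.3 count it as respiratory failure, Section 6.2 does not list it, and flowchart footnote f omits the non-rebreather settings listed in Section 4.5.2.

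**The case against.** The strongest reply is that little is lost in practice. The double asterisk sits on one row and one column. The ordinal scale goes on daily and again at day 28 for everyone, and vital signs, vasopressors and adverse events continue. A re-intubation could well qualify as a serious adverse event and be reported through day 28. If sites follow 4.5.5 there is no gap at all. The exposed outcomes are secondary, in a trial that Section 3.3 says is not powered for significance.

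Much of this stands, and it rules out several stronger readings that a reader might infer:

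- **That free-day outcomes or relapse cannot be determined.** This does not follow. The daily scale may recover them if its levels are fine enough. The supportable statement is that two outcomes are not assured.
- **That carry-forward under Section 6.2 turns relapsed patients into successes.** This would need a relapse, a missing day-28 respiratory record, a missing day-28 ordinal score and no usable later daily score, all in one patient. The End of Study column of the flowchart, headed Day 28 or discharge, also marks respiratory status, so on that reading a discharged patient has a record at discharge. And with unknown levels, a 2-point gain may leave a patient on a device that still counts as failure.
- **That a number of misclassified patients, or a difference by arm, can be stated.** The documents give no rate of improvement or re-escalation, and study staff are blinded.

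The reply does not remove the conflict between the two schedules. Nor does it show that the scale carries device-level information. Adverse-event reports describe events, not the device in use on each day.

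**Conclusion.** The point holds as an internal contradiction with a bounded consequence. Appendix 1 and Section 4.5.5 prescribe different collection of respiratory status, and the event that triggers the difference is not defined in the supplied text. If sites follow the footnote, the device record on this row ends at the first 2-point gain; a last record on day 8 leaves 19 of 24 follow-up days without an entry. Ventilator-free and respiratory failure-free days then depend on an ordinal scale of unknown resolution. The day-28 primary outcome is touched only to the extent that discharged patients are classified at day 28 from that same scale.

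This rests on two conditions: that at least some sites follow the flowchart, which Section 4.5 entitles them to do, and that the scale's levels are not set out in material removed from the supplied text. If the scale separates all four devices from lesser support, the loss is largely recoverable, but the two schedules would still need to be reconciled.

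**What to change.** 1. In Appendix 1, footnote \*\*, delete the clause that ends collection at a 2-point ordinal improvement, so that the footnote agrees with Section 4.5.5.
2. Record the highest respiratory support device on each inpatient day through day 28, with categories that include non-rebreather mask, high-flow nasal cannula, non-invasive positive pressure ventilation and mechanical ventilation.
3. For discharged patients, record the device in use at day 28 at the ordinal-scale contact that Section 4.5.6 already plans.
4. State the ordinal scale's levels and direction in the protocol. If a 2-point gain is kept for any other purpose, state the assessment from which it is measured.

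The cost is one amended footnote, one case report form field, a printed scale, and a few minutes of chart abstraction per inpatient day after improvement. No treatment or visit changes.
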